### **Sample size calculation**

Quadriceps muscle endurance and strength will be employed as the primary outcome for sample size estimation. Based on our recent pilot result, the difference in extension strength between atrophy and non-atrophy group was 30 Nm (SD 60 Nm), providing an effect size 0.42. Hence, with effective size set at 0.42, the estimated sample size will be 64 (32 for each arm) will be able to achieve 90% confidence to detect the difference between the two groups with a significance level (alpha) of 0.05 using a two-sided sample test. With an inclusion of 25% dropout rate, we have modified the total sample size to be 80 (40 for each arm). Thus, 80 subjects will be recruited in total.

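### Thirty-two patients per arm give about 38% power at the stated effect size of 0.42 (50% at 30/60 = 0.50), not 90%, and 80 does not cover 25% dropout

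*Protocol*

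**What the plan says.** Everything is in one paragraph of the protocol, Sample size calculation.

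- **Outcome:** "Quadriceps muscle endurance and strength will be employed as the primary outcome for sample size estimation".
- **Effect:** in the pilot, "the difference in extension strength between atrophy and non-atrophy group was 30 Nm (SD 60 Nm), providing an effect size 0.42".
- **Size and power:** "with effective size set at 0.42, the estimated sample size will be 64 (32 for each arm) will be able to achieve 90% confidence". The target is a difference between the two groups, "with a significance level (alpha) of 0.05 using a two-sided sample test".
- **Dropout:** "With an inclusion of 25% dropout rate, we have modified the total sample size to be 80 (40 for each arm").

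Randomization and blinding confirms 1:1 allocation. Data processing and analysis names a paired-sample t-test or the Wilcoxon signed-rank test. It states no baseline adjustment and no baseline–outcome correlation.

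**The concern.** Three steps in the paragraph fail to follow from one another: from the pilot difference and SD to the effect size, from the effect size to 64 patients, and from 64 to 80. The second matters most. Thirty-two per arm is far too few for 90% power at a standardised difference of 0.4 to 0.5.

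A further point concerns the source of the target. The 30 Nm is a gap between patients with and without atrophy, not a PEMF-versus-sham difference. The protocol is open about where the number comes from. It does not say that using it as the treatment target assumes a benefit as large as that whole gap.

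The power figure tells an ethics committee, a funder and later readers what a null result would mean. With 90% power, a null result would be fair evidence against an effect of the target size. With 38% to 50% power it would say little, and the stated 90% invites over-interpretation.

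**Working it through.** **Inputs** (all from the protocol, Sample size calculation): difference 30 Nm; SD 60 Nm; stated effect size 0.42; 32 per arm; two-sided alpha 0.05; 90%, read as power because alpha is given separately; 25% dropout; 80 in total.

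**1. Effect size.** d = difference / SD = 30/60 = 0.50. To obtain 0.42, either the SD must be 30/0.42 = 71.4 Nm or the difference must be 0.42 × 60 = 25.2 Nm. The text does not show which input is off, so both values of d are carried forward.

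**2. Power with 32 per arm.** Two-sample t-test, 62 degrees of freedom, two-sided critical value 1.999, noncentrality d × √(n/2) = d × √16 = 4d.

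- d = 0.42: noncentrality 1.68, power 38.0% (normal approximation 39.0%).
- d = 0.50: noncentrality 2.00, power 50.4% (normal approximation 51.6%).

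The stated 90% is not reproduced.

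**3. Size needed for 90%.** The normal approximation is n per arm = 2(1.960 + 1.282)²/d².

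- d = 0.42: 119.1, so 120 per arm; exact t, 121 (242 in total).
- d = 0.50: 84.1, so 85 per arm; exact t, 86 (172 in total).

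**4. Detectable difference.** With 32 per arm, 90% power is reached at d = 0.823, which is 0.823 × 60 = 49.4 Nm.

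**5. Dropout.** 64 × 1.25 = 80, which is the figure used. But 80 × 0.75 = 60 (30 per arm), and 64/0.75 = 85.3, so 86 would be needed. Equivalently, 80 covers a loss of 16/80 = 20%.

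**6. Power under other evaluable numbers** (two-sided 5%, unadjusted):

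| Evaluable per arm | d = 0.42 | d = 0.50 | 90%-detectable difference, SD 60 Nm |
|---|---|---|---|
| 30 (25% lost from 80) | 36.0% | 47.8% | 51 Nm |
| 32 (20% lost from 80) | 38.0% | 50.4% | 49 Nm |
| 40 (no loss) | 45.8% | 59.8% | 44 Nm |

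**7. Attempts to recover 64.**

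- One-sided 5% test, 32 per arm: 51% (d = 0.42) or 63% (d = 0.50). Not 90%.
- One-sample or paired t-test at 0.42: 62 pairs are needed for 90%, and 64 pairs give 91.1%. This is close, but it is a within-patient test and cannot be split into two arms of 32.
- 0.42 read as Cohen's f: for two groups d = 2f = 0.84, which needs 31 per arm and gives 91.1% at 32. This is also close, but at SD 60 Nm it means 0.84 × 60 = 50.4 Nm, not 30 Nm.
- d = 0.50 at 80% power: 64 are needed, but per arm, not in total.

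The second and third routes could explain the 64, though that is inference. None of the four is the calculation the protocol describes.

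**The case against.** **Baseline adjustment.** This is the strongest defence. Strength is measured before treatment, and an analysis plan not shown here may adjust for it. With baseline–outcome correlation r, the effective effect size becomes d/√(1 − r²). At 32 per arm, for assumed values of r:

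| r | d = 0.42 | d = 0.50 |
|---|---|---|
| 0.6 | 54% | 69% |
| 0.7 | 64% | 79% |
| 0.8 | 79% | 91% |

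So the figures of 38% and 50% apply to an unadjusted comparison and should be labelled so. But reaching 90% needs r of about 0.79 (d = 0.50) or 0.86 (d = 0.42). The protocol gives neither an adjustment nor a correlation, and its formula inputs are those of an unadjusted comparison. The defence limits the size of the shortfall but does not support the sentence as written.

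**The dropout error is small.** This is true. It is six patients (80 against 86) and costs 2 to 3 percentage points of power. It belongs in the same correction but is not the main problem.

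**The pilot data are unseen.** The 60 Nm might be one group's SD, with a pooled SD nearer 71 Nm. That would rescue 0.42 but not the power, which would then be the lower figure, 38%.

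**The target difference is a planning judgement.** This is fair. Borrowing 30 Nm is not an arithmetic error. What is missing is a statement of what it assumes.

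**Conclusion.** The concern holds. On the protocol's own inputs, an unadjusted two-sided 5% comparison of 32 against 32 has 38.0% power at 0.42 or 50.4% at 0.50, against the stated 90%. If 25% of 80 drop out, these fall to 36.0% and 47.8%. The chance of missing the target effect is therefore 50% to 64% across these cases, not 10%. The stated effect size does not follow from its own numerator and denominator, and 80 does not protect 64 evaluable patients against 25% loss.

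The conclusion assumes only that the confidence figure means power and that the comparison is between the two randomised arms, as the text says. Which of 0.42 and 0.50 was intended cannot be settled from the document, but 90% fails under both. The paragraph must be corrected.

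**What to change.** Rewrite the Sample size calculation paragraph, keeping N = 80:

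1. Give the effect size as 0.50, or correct the 30 Nm or 60 Nm if 0.42 is right.
2. Replace the 90% confidence claim with the power the design has for an unadjusted two-sample comparison, or with the detectable difference.
3. Match the dropout rate to the evaluable number. Either 20% dropout leaves 64 evaluable (power 50% at d = 0.50 or 38% at 0.42; 90% power for about 49 Nm at SD 60 Nm), or 25% dropout leaves 60 (48% or 36%; about 51 Nm).
4. State that 30 Nm is a target difference taken from atrophy versus non-atrophy patients, and why it is a reasonable target for PEMF against sham.
5. If the primary analysis is to be a baseline-adjusted ANCOVA, say so and quote power under an explicit correlation with its source.

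This costs one paragraph and no extra patients, but the stated power becomes less favourable and the underlying power does not change. If the sponsor wants to keep the 90% for an unadjusted comparison, the number randomised with 25% dropout would be about 230 at d = 0.50 (172/0.75) or 324 at d = 0.42 (242/0.75 = 322.7, rounded up to 162 per arm).

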### **Data processing and analysis**

The data obtained in the tests will be analyzed using Statistical Package for Social Science (SPSS) (IBM SPSS ver.26). For parametric data, a paired-sample t-test will be used. Wilcoxon signed-rank test will be used to analyze the data sets if they are non-parametric. The alpha level will be set at 0.05 for all statistical tests.

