## **Objective**

To conduct a double-blinded, randomized controlled trial to investigate the effects of PEMF treatment during the late postoperative period on quadriceps muscle strength and muscle weakness in ACL injured patients.

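### The only tests named are paired, so the analysis as written contains no PEMF-versus-sham comparison and invites ordinary recovery to be read as a PEMF effect

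*Protocol*

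**What the plan says.** The Protocol's Data processing and analysis section is four sentences long. Apart from the software, it gives two tests and an alpha level. Its main test is given as follows: "For parametric data, a paired-sample t-test will be used". The fallback, for data judged unsuitable for that test, reads: "Wilcoxon signed-rank test will be used to analyze the data sets if they are non-parametric". On the significance level the section adds only this: "The alpha level will be set at 0.05 for all statistical tests". Nowhere does the protocol name an independent-samples test, an analysis of covariance, a group-by-time model or a mixed model.

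The rest of the protocol describes a parallel-group trial. The Objective is a "double-blinded, randomized controlled trial to investigate the effects of PEMF treatment during the late postoperative period". Subject recruitment and Randomization and blinding allocate 80 participants 1:1 in blocks of 10, with no matching of individuals. The Intervention section gives controls a sham exposure on the same device. Sample size calculation aims to "detect the difference between the two groups with a significance level (alpha) of 0.05 using a two-sided sample test".

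**The concern.** A paired test needs two measurements that belong together. In this trial those are a participant's own values before and after treatment, or the two legs of one participant. A before-after test in the PEMF arm asks whether that arm changed, not whether it changed more than the sham arm. Used across arms, it would have to pair unrelated people arbitrarily, which is invalid. Followed literally, the section yields no treatment effect estimate, no confidence interval for one and no test of PEMF against its control.

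This design is especially exposed. The Background says rehabilitation itself restores strength over time. Eligibility requires a limb symmetry index below 70% at 4 months, so some regression to the mean is likely, and patients who do not comply with rehabilitation are excluded. Improvement over the 8 treatment weeks is therefore expected in both arms. The Hypothesis is also worded as a gain in strength with no comparator named, so a significant within-arm gain could easily be taken as confirming it. The sham arm exists to remove this error, and the named tests do not use it.

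**Working it through.** **1. Does the stated sample size point to a paired or a two-group test?**

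Inputs from Sample size calculation: effect size 0.42, two-sided alpha 0.05, 90% (called confidence, evidently power), 64 evaluable, 32 per arm.

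- Two-group formula: n per arm = 2 × (1.960 + 1.282)² / 0.42² = 2 × 10.51 / 0.1764 ≈ 119.1, so 120 per arm or 240 in total. The stated 64 is not reproduced.
- Paired or one-sample t-test with the same inputs: 62 pairs (61.5 before rounding). This is close to 64, but it would mean 64 pairs in one group, not 32 in each of two.

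The text of that section describes a two-group contrast. The only calculation tried that comes near its number is a paired one. The size of the trial is a separate matter; the result is shown here because the same confusion of designs may lie behind both sections.

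**2. What do the named tests do if PEMF has no effect?**

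Inputs:
- SD 60 Nm and 32 evaluable per arm, from Sample size calculation. The SD comes from a pilot contrast of atrophy and non-atrophy groups, so using it for trial participants is itself an assumption.
- Common recovery in both arms of 10, 20 or 30 Nm over 8 weeks: assumed.
- Pre-post correlation r of 0.7 or 0.8: assumed.

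Formulas:
- SD of change = 60 × √(2(1 − r)). For r = 0.7 this is 60 × √0.6 = 46.5 Nm; for r = 0.8 it is 60 × √0.4 = 37.9 Nm.
- Standardised change = recovery / SD of change. For 20 Nm and r = 0.7: 20 / 46.5 = 0.43, noncentrality 0.43 × √32 = 2.43.
- P = probability that the paired t-test (32 pairs, two-sided 0.05) is significant, from the noncentral t distribution.
- The arms are independent, so PEMF significant and sham not has probability P(1 − P), which cannot exceed 25%.

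| Recovery, r | SD of change | PEMF arm significant | PEMF significant, sham not |
|---|---|---|---|
| 10 Nm, 0.7 | 46.5 | 22% | 17% |
| 20 Nm, 0.7 | 46.5 | 65% | 23% |
| 20 Nm, 0.8 | 37.9 | 82% | 15% |
| 30 Nm, 0.8 | 37.9 | 99% | 1% |

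Simulation of 20,000 null trials per setting agrees to within about one percentage point. A two-sample test on change rejects in about 5% throughout.

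A second set of assumptions (common gain of 0.3 or 0.5 SD, r = 0.5) gives about 37% or 78% for the PEMF arm and about 23% or 17% for the discordant pattern, again against about 5% for a between-arm test.

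**3. What would a between-arm analysis gain from baseline strength?**

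Adjusting for baseline multiplies the residual variance by 1 − r². The protocol's 30 Nm over 60 Nm is 0.50, although it states 0.42 ("was 30 Nm (SD 60 Nm), providing an effect size 0.42"), so both are shown for 32 per arm:

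- Effect 0.50: unadjusted power 50%; adjusted 69%, 79% and 91% at r = 0.6, 0.7 and 0.8.
- Effect 0.42: unadjusted 38–39%; adjusted 49% to 80% over r = 0.5 to 0.8.

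**The case against.** The best reply is that the intention is clear. The sample size section speaks of a difference between the two groups, the analysis section is brief and does not tie either test to a contrast, and a statistical analysis plan that is not shown may supply the right test. That the intention is a between-group comparison can be granted. But this is not mere silence left for a later plan: the protocol names specific tests, and they do not fit its own design.

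The protocol also sets no rule that within-arm significance counts as efficacy. That is correct, and the error rates above apply only if within-arm results are read that way. It remains the natural reading when these are the only tests named.

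Paired tests do have legitimate uses here: pain scores before and after each session, and the injured leg against the uninjured one. The fault is naming nothing else.

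The recovery and correlation values are not in the protocol, and the Background notes that some compliant patients fail to regain muscle mass. The percentages are therefore illustrative. The direction is not in doubt: any real average recovery takes the within-arm rejection rate above 5%.

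Finally, covariance adjustment over a plain two-sample test is a matter of efficiency. The minimum correction is any valid between-arm test.

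**Conclusion.** The concern holds and must be fixed. The analysis section specifies tests that cannot answer the question for which the trial is randomised, blinded and sized. If within-arm significance is taken as evidence of efficacy, a PEMF device with no effect would appear to work in about 22% to 99% of trials. The pattern of PEMF significant and sham not would arise in about 1% to 23%, against the nominal 5%. These ranges assume 32 evaluable per arm, SD 60 Nm, equal recovery of 10 to 30 Nm in both arms and a pre-post correlation of 0.7 to 0.8. The mismatch between the named tests and the design depends on none of these assumptions.

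**What to change.** Replace the paired tests as the primary analysis with a between-arm comparison of injured-leg quadriceps extension peak torque at 8 weeks after the start of treatment. Use analysis of covariance with arm and baseline peak torque as terms, or a mixed model over the 4-week, 8-week and 12-month visits with baseline as a covariate and a group-by-time term. Report the adjusted PEMF-minus-sham difference with its 95% confidence interval. The protocol names both endurance and strength as primary and fixes no primary time point, so the sponsor should confirm this choice of variable and visit.

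If a rank-based sensitivity analysis is wanted, use a two-sample method (Mann-Whitney or rank analysis of covariance) in place of the signed-rank test. Keep paired tests for within-arm or between-leg description, and state that they carry no inference about efficacy.

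The analysis change costs only wording: Follow up time points already schedules the strength measurements, and SPSS fits these models. It does oblige the sponsor to check the sample size against the new test. At the stated effect of 0.42, an unadjusted two-sample test has about 38–39% power with 32 per arm and 46–47% with 40 per arm, far below the intended 90%.

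### The test switches with the look of each data set, so strength may be tested on means in one arm or visit and on ranks in another, although the trial is planned on a between-group difference in Nm

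*Protocol*

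**What the plan says.** The analysis rule is in the protocol's Data processing and analysis section. The first branch is "For parametric data, a paired-sample t-test will be used"; the fallback is "Wilcoxon signed-rank test will be used to analyze the data sets if they are non-parametric". The section closes with "The alpha level will be set at 0.05 for all statistical tests". It does not say what makes a data set non-parametric, and it does not name the hypothesis under test as mean change or anything else.

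The Sample size calculation is on another footing. It takes quadriceps endurance and strength as primary and starts from a pilot finding that "the difference in extension strength between atrophy and non-atrophy group was 30 Nm (SD 60 Nm". It then aims to "achieve 90% confidence to detect the difference between the two groups", at a "significance level (alpha) of 0.05 using a two-sided sample test". That is a contrast of two groups, on a scale of means in Nm.

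Under Follow up time points, strength is measured before treatment, at 4 and 8 weeks after its start, and at 12 months post-op, in two arms.

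**The concern.** The plan states a switch; it does not merely leave a detail open. A later document could say which normality check applies and at what level, but the choice between means and ranks would still follow the data. Two consequences need examining.

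- **Mixed scale.** One variable gives several data sets (two arms, several visits). If each is judged on its own, some results concern means and others ranks. They cannot then be compared with each other or set against the Nm scale of the sample size.
- **Fallback under skew.** As a test of mean change, the signed-rank test needs paired differences that are symmetric about zero under the null. Skewed differences are one common reason to call data non-parametric, and they break that condition. The fallback may then be further from its nominal level than the t-test it replaces.

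**Working it through.** **Inputs from the protocol.** Alpha 0.05, two-sided; 32 evaluable and 40 randomised per arm; paired t-test or signed-rank test. The sample-size arithmetic is a separate matter. Only its scale (Nm) and its contrast (two groups) are used here.

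**Assumptions, since the protocol gives neither.** The switch is a Shapiro-Wilk test at 0.05 on the paired differences. Skewed changes are gamma-shaped with shape k, centred to a true mean of zero, so skewness = 2/√k: k = 16 gives 0.5, k = 4 gives 1, k = 2 gives 1.4, k = 16/9 gives 1.5, k = 1 gives 2.

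**Statistics.** With d the paired differences, t = mean(d)/(SD(d)/√n). For signed-rank, z = (W − n(n+1)/4)/√(n(n+1)(2n+1)/24), where W is the sum of the ranks of |d| over the positive d. Reject if |z| > 1.96.

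**Step 1: within-arm rejection rates with no true change.** 10,000 simulated data sets per setting; the simulation standard error at 5% is √(0.05 × 0.95/10,000) = 0.22 percentage points. Each cell shows n = 32 / n = 40, in %.

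| Differences | t-test | Signed-rank | Switch | Sent to signed-rank |
|---|---|---|---|---|
| Normal | 4.9 / 5.4 | 5.1 / 5.2 | 5.1 / 5.4 | 5.0 / 5.1 |
| Skewness 0.5 | 5.3 / 5.0 | 6.2 / 6.0 | 6.1 / 5.7 | 15.0 / 18.0 |
| Skewness 1 | 5.6 / 5.7 | 7.6 / 8.5 | 7.8 / 8.3 | 48.1 / 57.3 |
| Skewness 1.5 | 6.0 / 6.2 | 11.2 / 12.8 | 11.2 / 12.8 | 83.1 / 91.9 |
| Skewness 2 | 7.1 / 6.8 | 16.7 / 19.4 | 16.7 / 19.4 | 97.5 / 99.5 |
| Symmetric, t with 3 df | 4.2 / 4.7 | 4.5 / 5.2 | 4.7 / 5.2 | 48.5 / 55.6 |
| Symmetric, Laplace | 4.8 / 4.6 | 4.9 / 4.8 | 5.0 / 4.8 | 37.4 / 44.2 |
| Lognormal pre and post, independent, same distribution | 3.6 / 4.3 | 4.4 / 4.8 | 4.5 / 4.7 | 78.2 / 85.7 |

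The stated 0.05 is recovered for normal differences and for every symmetric case, including skewed raw values with no change in distribution. It is lost only where the differences themselves are skewed. Repeat simulations of the switch at n = 40 gave 7.7% to 8.5% at skewness 1, 12.0% to 12.4% at 1.4, and 18.0% to 19.4% at 2.

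**Step 2: how often the scale is mixed.** If the check is run separately in each arm, at skewness 1 and n = 40 an arm goes to signed-rank with probability 0.573. The two arms then get different tests with probability 2 × 0.573 × (1 − 0.573) = 0.49, about half the time. In the normal case it is 2 × 0.051 × 0.949 = 0.10.

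**Step 3: the same kind of switch between arms.** Two-sample t-test or Mann-Whitney, 40 per arm, same distribution in both arms, 6,000 data sets per setting:

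| Data | t-test | Mann-Whitney | Switch | Better of the two |
|---|---|---|---|---|
| Normal | 5.0% | 4.6% | 5.1% | 5.8% |
| Skewness 1.4 | 4.7% | 4.3% | 4.4% | 6.1% |

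Repeat runs put the between-arm switch at 4.7% to 5.9%. The error rate is essentially unaffected, and the plain t-test holds its level without a switch.

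**The case against.** The case for leaving this alone is substantial.

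- **The level.** A reader might infer that the 0.05 level fails outright. The documents do not support that. The section does not name mean change as the null; under no change in distribution the differences are symmetric and the signed-rank test is valid. The protocol gives no skewness for strength changes, and at skewness 0.5 the excess is about one percentage point.
- **When the fallback is used.** A reader might infer that it is reserved for skewed changes. Ordinal scores such as Tegner, or heavy-tailed symmetric differences, can equally trigger it. In the symmetric continuous cases simulated it stays near 5%.
- **Picking the better result.** A reader might infer that the analyst may see both results and choose. The text ties the test to the type of data, not to p-values, and a statistical analysis plan that is not shown may fix the criterion, its timing and the level at which it applies.
- **Carry-over to a between-arm test.** A reader might infer that the inflation persists there. It does not (Step 3).
- **Estimate in Nm.** A signed-rank analysis can report a Hodges-Lehmann shift in Nm, and the 30 Nm is a pilot atrophy contrast, not a stated PEMF effect.

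All of this stands, and it confines the concern. It does not remove the stated dependence of the test on the data or the resulting mixture of means and ranks. A Hodges-Lehmann shift also equals the mean change only under symmetry, so it does not restore a common quantity across data sets.

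**Conclusion.** The point holds in a limited form and is minor. The protocol lets the appearance of each data set decide between a test on means and a test on ranks, while the trial is sized on a two-group difference in Nm. If the check is made arm by arm, which the text permits but does not state, moderate skewness would give the two arms different tests about half the time.

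The error-rate part is conditional. It applies to within-arm testing, with skewed differences and mean change as the target, and its size rests on the assumed gamma shapes and Shapiro-Wilk switch: from about 6% at skewness 0.5 to 18–19% at skewness 2 with 40 patients, against about 5–7% for the t-test alone. For the PEMF-versus-sham question there is no material inflation, and the argument is consistency of the estimand. The larger defect in the same section is that both named tests are within-subject, so neither compares the arms; removing the switch alone would not cure that.

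**What to change.** In Data processing and analysis, replace the switch with one named, mean-based comparison of PEMF with sham for strength. For example: the difference in mean extension strength in Nm between arms, from a linear model adjusted for baseline, with its confidence interval, used whatever a normality check shows. Report a rank test as a sensitivity analysis only. For outcomes expected to be skewed, such as IPAQ or the myokines, name a log scale or bootstrap interval in advance.

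Make the change in the same edit that replaces the within-subject tests by between-arm ones, so that a new switch between a t-test and Mann-Whitney is not written in. The cost is wording only: no extra patients, visits or measurements. The downside is slightly less power than a rank test if strength proves heavy-tailed, which the sensitivity analysis would show.

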PEMF therapy has been demonstrated to enhance cellular activity related to tissue healing (7), and offer beneficial effects such as pain relief, anti-inflammation and oedema resolution (8). Numerous variables in the delivery of PEMF signals (i.e., magnetic flux, frequencies, signal curve, polarity, etc) may have specific biological implications. Our group ([name]) showed that brief 10-minute exposure of 1.5mT amplitude of PEMF (Quantum Tx) on myoblast in-vitro could activate myogenesis. It is done so by stimulating the TRPC-1-mediated calcium entry and downstream factors as well as PGC-1 $\alpha$ , this mechanism (mentioned above) is similar to the myogenesis in exercise (4). PGC-1 $\alpha$  gene expression is influenced by every major signaling pathway that is activated in a contracting muscle (9). Additionally, it plays an important role in regulating the production and secretion of myokine. Therefore, PEMF exposure on top of regular exercise training, may promote the secretion of myokine and in turn promote muscle regeneration.

Our study will examine the efficacy of PEMF treatment introduced at the late postoperative period. It helps to set up the treatment regime for the PEMF device to impose myogenic effects, including exposure time per session, the number of treatment sessions and the duration of treatment. To our best knowledge, this proposed study aims to apply PEMF as an intervention for patients with myokine-mediated persistent quadriceps muscle atrophy after ACLR. In turn, it would be the first study to examine the correlation between PEMF and post-operative quadriceps muscle endurance, strength and mass. Apart from the quadriceps muscle, we will also examine the bone microarchitecture changes correlating to the PEMF treatment in the post-operative period.

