#### Serum myokine evaluation

Phlebotomy (5ml) will be performed at pre-op, before PEMF treatment, at 4- and 8- weeks after commencement of treatment, and at post-op 12 months. The serum will be prepared by centrifugation and kept in a -80o freezer until use. Quantitative analysis for myokines and proteins related to muscle metabolism will be performed by Human Myokine Magnetic Bead Panel (Millipore) with Bioplex-200 bead-based suspension assay system (LKSIIHS core facilities), or enzyme-linked immunosorbent assay (ELISA). These include Brain-derived neurotrophic factor (BDNF), Fibroblast growth factor-21 (FGF-21), Interleukin-6 (IL-6), IL-15, Irisin, Myostatin (MSTN)/GDF8, Insulin-like growth factor 1 (IGF-1), FGF-2, IL-8, Follistatin, Musclin, Myonectin, Decorin, Meteorinlike, Osteopontin, Secreted protein acidic and rich in cysteine (SPARC), Klotho, Procollagen type III N-terminal peptide (P3NP), and C-terminal of troponin T1 (TNNT1).

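### The flat 0.05 rule covers a secondary panel of at least 19 serum myokines at repeated visits, so an isolated significant myokine would be weak evidence of a PEMF effect

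*Protocol*

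**What the plan says.** The Protocol's section on data processing and analysis sets one significance rule: "The alpha level will be set at 0.05 for all statistical tests". It names two tests: "For parametric data, a paired-sample t-test will be used", and "Wilcoxon signed-rank test will be used to analyze the data sets if they are non-parametric". The sample size section confirms that the level is two-sided.

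The section on serum myokine evaluation lists the analytes, from "These include Brain-derived neurotrophic factor (BDNF), Fibroblast growth factor-21 (FGF-21), Interleukin-6 (IL-6), IL-15, Irisin, Myostatin (MSTN)/GDF8" to "Klotho, Procollagen type III N-terminal peptide (P3NP), and C-terminal of troponin T1 (TNNT1"). The list has 19 names and is introduced as an inclusion list, so 19 is a minimum. Blood is drawn before surgery, before PEMF, at 4 and 8 weeks of treatment, and at 12 months after surgery. The section on follow-up time points agrees on baseline, 4 and 8 weeks, but its 12-month list does not include blood.

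Myokines are part of the rationale. The Background says that "PEMF exposure on top of regular exercise training, may promote the secretion of myokine and in turn promote muscle regeneration". It also describes the target atrophy as myokine-mediated, and the Intervention section cites myokine release in support of the regimen. The primary outcome in the sample size section is quadriceps endurance and strength. Nowhere does the Protocol name a key myokine or key visit, label the panel exploratory, or give an adjustment for the number of analytes.

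**The concern.** Testing many analytes at several visits, each at 0.05, gives many chances of a false positive. The Protocol does not merely leave this open: it extends 0.05 to every test, and the myokine panel falls within that wording.

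What is at stake is how a secondary mechanistic result can be read. Because the rationale runs through myokine secretion, one significant analyte could easily be taken as support for the mechanism. Under the stated rule, nothing separates such a result from what chance would produce across the panel.

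**Working it through.** The plan gives no error rate for the panel as a whole, so there is no figure of its own to reproduce. Its only figure here is 0.05 per test.

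**Inputs from the Protocol**
- Two-sided level per test: 0.05.
- Analytes: 19 (BDNF, FGF-21, IL-6, IL-15, irisin, myostatin, IGF-1, FGF-2, IL-8, follistatin, musclin, myonectin, decorin, meteorin-like, osteopontin, SPARC, Klotho, P3NP, TNNT1).
- Visits after treatment starts: 2 by the follow-up section (weeks 4 and 8), or 3 by the myokine section (adding 12 months).

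**Assumptions, not in the Protocol**
- PEMF changes no analyte, and each analyte is compared between arms.
- Analytes are equally correlated, from 0 to 0.8.
- The same analyte at two visits is correlated 0.5 to 0.8.

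**Step 1. Number of tests and expected false positives**
- One visit: 19 × 0.05 = 0.95.
- Two visits: 38 × 0.05 = 1.9.
- Three visits: 57 × 0.05 = 2.85.

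These expected counts do not depend on the correlations.

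**Step 2. At least one p<0.05 if all tests were independent**, 1 − 0.95^k
- k = 19: 1 − 0.95^19 = 62.3%.
- k = 38: 1 − 0.95^38 = 85.8%.
- k = 57: 1 − 0.95^57 = 94.6%.

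The last two are upper reference points, since repeated measurements of one analyte are not independent.

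**Step 3. The same chance with correlated tests**, by simulating null normal test statistics

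| Visits | Analyte correlation | Between-visit correlation | At least one p<0.05 |
|---|---|---|---|
| 1 | 0 | – | 62% |
| 1 | 0.2 | – | 57% |
| 1 | 0.5 | – | 41% |
| 1 | 0.8 | – | 22% |
| 2 | 0 | 0.5 | about 83% |
| 2 | 0.5 | 0.5 to 0.8 | 56% to 62% |
| 2 | 0.8 | 0.8 | about 32% |
| 3 | 0.5 | 0.5 to 0.8 | 65% to 75% |

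The lowest figure, 22%, is still more than four times 5%.

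**Step 4. Effect of the fix**

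Benjamini-Hochberg orders the 19 p-values at one visit and declares significant those up to the largest k with p(k) ≤ 0.05 × k/19. If PEMF affects nothing, the simulated chance of any declaration is 3% to 5% for analyte correlations from 0.8 to 0. If only one analyte stands out, its threshold is 0.05 × 1/19 = 0.0026.

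**The case against.** **The SAP may deal with it.** Multiplicity in a non-primary biomarker panel is commonly left to the SAP, and the Protocol does not say that p-values will go unadjusted. The first part is fair. But a level of 0.05 for all tests is a stated rule, and its natural reading is no adjustment. An SAP that adjusted the panel would sit awkwardly with it.

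**The myokine result decides nothing.** A reader might infer that any single significant protein would count as proof of mechanism, or would be reported as the explanation of the strength result. The documents do not say so. The Objective and Hypothesis concern muscle strength and weakness only, and the Background says only that PEMF may promote myokine secretion. This objection stands, so the point is limited to how much weight an isolated hit can bear.

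**A false positive is not always likely.** A reader might conclude that the panel will usually produce one. That depends on correlations that the Protocol does not give. At one visit the chance is below half once the analyte correlation reaches 0.5. Over two visits it is below half at about 0.7 (43% to 49%). The three-visit figures need a 12-month blood sample that only one of the two sections lists. What survives is a rate well above 5% throughout the range examined.

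**The figures do not describe the tests as written.** This also stands. The only named tests are paired. If they are run within an arm, myokines may change through ordinary recovery, so the null need not hold even when PEMF does nothing. The rates above apply only to PEMF-versus-sham comparisons. Adjusting within-arm tests would not separate PEMF from recovery, which is why the fix has to name the comparison as well as the adjustment.

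**Conclusion.** The point holds as a modest one about a secondary family. The stated rule puts at least 19 analytes, at two or possibly three visits, at 0.05 each. Given no PEMF effect and between-arm comparison, the chance of at least one nominally significant result is 22% to 62% at one visit (analyte correlation 0.8 to 0). Over weeks 4 and 8 it is about 32% to 83% (between-visit correlation 0.5 to 0.8). The correlations are assumed. An isolated hit is therefore weak evidence of a myokine response.

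It would go too far to say that the trial cannot tell a true myokine response from chance. The data are not compromised, and a prespecified adjustment would restore a usable error rate. The primary strength conclusion does not depend on this point.

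**What to change.** In the data processing and analysis section, add wording to this effect: the serum myokine panel is a secondary outcome; each listed analyte is compared between PEMF and sham, not by paired tests within an arm, at one prespecified visit (for example 8 weeks, the end of treatment); the false discovery rate across the listed analytes at that visit is controlled at 5% by Benjamini-Hochberg; myokine results at other visits are exploratory and are reported as estimates with 95% confidence intervals, without claims of significance. Leave the alpha for the other outcomes as stated.

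Fix the analyte list, so that the number of comparisons is known, and reconcile the two sections on whether blood is taken at 12 months.

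The choice of week 8 and of false discovery control is a reasonable option, not the only one; Bonferroni within the panel would be stricter. The change costs a few sentences and no additional patients, samples or assays. Its downside is lower power for an effect confined to one analyte, which would need about p<0.0026. The loss is smaller if several myokines respond together, because the Benjamini-Hochberg threshold rises with each further small p-value.
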